The potential risks to subjects are anticipated to be minimal, and the anticipated benefits to patients enrolled in the study are potentially high. The majority of those who participate in aerobic exercise are expected to show an improvement in cognitive function, physiological status, aerobic capacity and QOL. Because CI and physical inactivity contributes to physical function decline and poor clinical outcomes in persons with HIV, improvement of physical function has the potential to significantly reduce the burden associated with this disorder and has potentially cost savings benefits. Based on our previous experience, we anticipate that the Let's Flex group may have an improvement in psychological functioning and QOL as a result of the contact with the research team members, but it will likely be of shorter duration than the intervention groups, and have no benefit on any of the other outcome variables. In addition, potentially Let's Flex participants may improve in HIV self-care behaviors based on the additional knowledge and education provided in the education sessions.

The potential knowledge to be gained from this study include a better understanding of the underlying mechanisms that contribute to CI and the influence of an aerobic exercise program on cognition, aerobic capacity and novel biomarkers. Moreover, testing a home-based intervention may increase future scalability and uptake of the intervention if efficacious.

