Group Motivational Interviewing (MI) (4 sessions) -MI groups will occur after the second visit and within 4 weeks. Each intervention group and attention control arm at each clinic will attend 4 separate group intervention sessions for 1.5 hours for 4 consecutive weeks. Participants will have initiated their individualized home-based program by the first group. Groups will consist of 4-8 members and content will focus on the rationale for aerobic exercise for the intervention group and stretching for the attention control arm. The content of the intervention group will focus on reducing blood pressure, lipids, CVD risk, enhancing muscle oxidation and function, reducing risk for physical function decline, barriers to exercise, finding time for exercise, how to set short and long term exercise goals, and use of self-monitoring (pedometers, Fitbits, polar heart watches, perceived exertion) to improve exercise engagement in the intervention group. In the attention control arm the focus will be on flexibility and stretching. MI strategies will be employed in the group discussions to foster commitment and confidence for behavior change and to help participants explore and resolve ambivalence about incorporating exercise or stretching. It is expected that the group sessions will promote effective problem solving as participants discuss challenges and responses to these challenges for integrating healthier lifestyle behaviors. During the group sessions, the research staff member(s) will review step calendars, download polar HR monitors for adherence and intensity level, review pedometer and/or Fitbit step data for the prior week in the intervention group and the attention control arm as well as monitor exercise intensity and duration based on these data in the intervention group. Once the 70% intensity level is achieved, the duration of exercise will be progressed at 5-10 minute intervals to reach a maximum of 60 minutes, 5 times per week. Weight and healthy messages using MI to set goals for exercise and healthy lifestyles will also be included for the intervention group and goals for flexing/stretching for the attention control arm. Attendance at all sessions will be

emphasized; however, if absent from a session, participants will receive phone calls and encouraged to attend a make-up session.

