The potential risks associated with the Let's Move intervention are anticipated to be minimal. Any potential cardiovascular (CV) events that poses risk to the participant is anticipated to be detected during the modified Balke or Bruce maximal treadmill test. In addition, the duration of walking will be limited to 30 minutes during the first 2 weeks and at an intensity level (60%) that is not likely to result in any adverse CV events; if necessary participants can rest as needed until the 30 minute duration of walking is completed. Participants will wear a Polar HR monitor or a Fitbit so that HR and intensity level can be closely monitored. Participants in the study will be provided with detailed instructions on self-monitoring HR, BP and symptoms associated before, during and after walking. Each participant will be provided with a target heart rate range to stay within during the study period. Participants will be instructed to wear the Polar HR monitor or Fitbit during each exercise session. The participants will take their HR, and BP (if machine available) and weight prior to and after each walking session and record it in their walking calendar. Participants will be instructed to call the research staff if their BP or HR is outside their normal range. If participants are symptomatic, experience increased shortness of breath over the previous 24 hours, they will be instructed not to exercise. The participants will be instructed to take their medications as usual prior to exercise and instructed on proper attire for exercising. Demonstrations and return demonstrations of the Polar HR monitor or Fitbit will ensure they know how to wear the monitors (Polar HR monitors specifically around the chest) as well as trouble shoot when either of the monitors does not display correctly. They will be instructed that if their HR approaches within 5-10 beats of the target HR range to slow the walking pace down. In addition, they will be instructed to monitor their RPE using the Borg 6 to 20 scale, and to keep their RPE at 12-13 during the initial weeks and to gradually progress with instructions to 15 as stipulated in the protocol. Participants in the intervention groups will be advised to carry a cell phone when they walk at home in the event of an emergency or sudden event. Specifically, participants will be instructed to slow their pace if their HR increases to near THR as previously noted or if they become short of breath. Participants who have ischemic heart disease and prescribed nitroglycerin (NTG) will be instructed to carry their NTG with them during each walking sessions. If chest pain occurs during exercise, the participants will be told to stop exercising and to take a NTG as directed by their cardiologist. The participant will also be instructed if the chest pain continues to sit down and to call a relative or friend and to take another NTG if the chest pain does not subside. If the chest pain continues and is not relieved by NTG within 10 minutes they will be instructed to call 911. If the participant becomes moderately to severely dyspneic where they cannot talk while walking they will be instructed to stop walking until the dyspnea subsides. If the dyspnea continues once they have stopped walking for several minutes they will be instructed to call a relative or friend; if not dissipated they will be instructed to go the nearest emergency room. If a participant becomes dizzy while walking they will be asked to sit down and to get up slowly once the dizziness passes. In our previous and ongoing work with heart failure patients and family caregivers, there were no adverse events reported for walking at the 60-70% intensity levels using a very similar protocol. If symptoms are present at current intensity level or duration of walking the participant will not be progressed until exercising at current level with RPE at 15 or below for 45 minutes. This will better ensure the participant is not progressed too rapidly.

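### As published, the home-walking symptom scripts contain no step to inform the study, and a symptom first mentioned at a monthly T2–T3 call would usually surface after the one-week limit

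*Combined protocol and SAP*

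**What the plan says.** The home-walking instructions are in section 5, under Risks/Discomforts for the Let's Move intervention.

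- **Chest pain:** "the participants will be told to stop exercising and to take a NTG as directed by their cardiologist". If it continues, the walker sits down, phones a relative or friend and takes a second dose. If it is unrelieved within 10 minutes, the walker calls 911.
- **Dyspnea that prevents talking:** "they will be instructed to stop walking until the dyspnea subsides". If it persists, the walker phones a relative or friend, then goes to an emergency room.
- **Dizziness:** "If a participant becomes dizzy while walking they will be asked to sit down and to get up slowly once the dizziness passes".
- **Before a session:** "If participants are symptomatic, experience increased shortness of breath over the previous 24 hours, they will be instructed not to exercise".
- **Progression:** "If symptoms are present at current intensity level or duration of walking the participant will not be progressed until exercising at current level", with a limit on perceived exertion.
- **Contacting the study:** "Participants will be instructed to call the research staff if their BP or HR is outside their normal range".

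The same paragraph promises instruction in self-observation: "Participants in the study will be provided with detailed instructions on self-monitoring HR, BP and symptoms associated before, during and after walking".

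Scheduled contact is set out under the T1, T2 and T3 assessments in section 5. Calls are weekly from the end of the motivational interviewing groups to T1, bi-weekly from T1 to T2, and monthly from T2 to T3. Their stated content is exercise frequency, intensity, time and type, then progress, barriers and ways to keep the program going. Walking continues throughout.

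Section 8 has the IRB told of reportable events, and the NINR Program Officer told of adverse events, within one week of the event. Section 9 repeats the one-week limit and sends all adverse events to the safety committee chair.

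**The concern.** The scripts are explicit, so a walker can follow them to the letter and never tell the study, even after a 911 call or an emergency room visit. Under the treadmill procedures in the same section, chest pain or dizziness is passed to the study cardiologist. In unsupervised walking, no step takes the same symptom to anyone at the study.

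Two things are at stake. First, a walker whose exertional chest pain has settled, with pulse and blood pressure in range, could return to the next prescribed session before staff have heard of it. The staff's power to adjust the dose and the cardiologist's judgment both depend on a report. Second, the notification limit runs from the event, not from when staff become aware of it, so late awareness uses up the time allowed.

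The population adds to the concern. Under section 6, participants enter through a low verbal memory score on the MoCA or a weak Oral Trail Making Test B. Recalling and volunteering a transient symptom weeks later is a weak safeguard in this group.

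**Working it through.** **Step 1: look for another route by which staff would learn of a symptom promptly.**

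- Walking calendar (Risks/Discomforts) and step calendar (Table 7): heart rate, blood pressure if a machine is available, weight, perceived exertion and steps. No symptom field is listed.
- Fitbit and heart-rate monitors (Quality and fidelity): steps, heart rate and duration. No alert or review interval is stated.
- Calls (T1 to T3 assessments): barriers and progress are discussed, and the interventionist log records barriers. No adverse-event question is stated.
- Process Evaluation: staff record difficulties and issues that participants raise at sessions. This captures what is volunteered, when contact occurs.
- Study arms: participants hold project office phone numbers, but no symptom is named as a reason to use them.
- Progression rule: it presumes that staff know of symptoms but gives no step for telling them. Table 3 also reaches its final dose in weeks 9–12, so by T2 little scheduled progression remains to withhold.

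Each route may bring a symptom out. None requires a prompt report.

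**Step 2: compare the call interval with the one-week limit.** The plan gives no figure of its own to reproduce. Inputs from the documents are the call intervals, the 7-day limit, T2 at 28–30 weeks and T3 at 56–58 weeks. Assumptions: calls are evenly spaced, events fall evenly between calls, and a symptom is mentioned only at the next call. For an interval of g days, the share surfacing after 7 days is max(0, g − 7)/g, the mean wait is g/2 and the longest wait is g.

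| Phase | g (days) | Surfacing after 7 days | Mean wait (days) | Longest wait (days) |
|---|---|---|---|---|
| Weekly calls to T1 | 7 | 0% | 3.5 | 7 |
| T1–T2, if twice a week | 3.5 | 0% | 1.75 | 3.5 |
| T1–T2, if every two weeks | 14 | 7/14 = 50% | 7 | 14 |
| T2–T3, monthly | 28 | 21/28 = 75.0% | 14 | 28 |
| T2–T3, monthly | 31 | 24/31 = 77.4% | 15.5 | 31 |

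The T2–T3 phase lasts 26 weeks (56 − 30) to 30 weeks (58 − 28), about half of follow-up. Its result does not depend on what bi-weekly means. The weekly row covers only the period after the groups. Walking starts earlier ("Participants will have initiated their individualized home-based program by the first group"), and no weekly contact is stated between that start and the first group.

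**Step 3: sessions walked before the next T2–T3 call.** At five sessions a week, the mean is 14 × 5/7 = 10.0 to 15.5 × 5/7 = 11.1.

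**Step 4: vary the reporting assumption for T2–T3.** If a share u of participants phones unprompted the same day, the late share is (1 − u) × 0.750 to 0.774:

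- u = 0.25: 56 to 58%
- u = 0.50: 38 to 39%

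If instead nobody phones and the investigators need 1 or 2 days to notify, the share that misses the limit is:

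- 1 day: 1 − 6/28 = 78.6% to 1 − 6/31 = 80.6%
- 2 days: 1 − 5/28 = 82.1% to 1 − 5/31 = 83.9%

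**The case against.** The strongest reply is that this paragraph summarizes risk and is not the participant's instruction sheet. It promises detailed teaching on symptoms, and Quality and fidelity commits to protocol manuals and scripts for visits and groups. The consent pages were not available. Any of these may already tell walkers to phone. This stands, and it limits confidence.

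Screening also stands. Section 6 excludes a history of angina with activity, dizziness, dyspnea on moderate exertion, and ischemic changes on the baseline treadmill test. The cardiologist clears each participant before home exercise, and the plan reports no adverse events in similar walking work. Few events are expected, although new symptoms remain possible and the paragraph itself provides for walkers who carry nitroglycerin.

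The pre-session hold and the pulse check around each session also narrow the scenario of resuming too early. They do not remove it, because pain that has settled with normal readings is not clearly covered.

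On deadlines, the IRB limit covers reportable events, and a brief dizzy spell may not be one. The NINR limit in section 8 is worded for adverse events generally, so the point does not fall away.

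A reader might infer that symptoms have no way of reaching staff, or that three quarters of events will be reported late. The documents support neither. The Process Evaluation records and barrier discussions are real, if unprompted, routes, and the percentage is conditional on assumed reporting behavior with no event rate behind it. A reader might also infer that exercise should stop automatically after any such symptom. The gap shown is in reporting, and it does not justify a mandatory hold.

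**Conclusion.** The point holds as a reporting gap in the published text. The three symptom scripts omit the study, the only call trigger is an out-of-range reading, and no other stated route requires a prompt report. From T2 to T3, a symptom mentioned only at the next call would surface after seven days about three quarters of the time, with waits of up to 28 to 31 days. That figure rests on even spacing of events and calls and falls to about 38% if half of participants phone unprompted. It is a share of whatever events occur, and their number is expected to be small. Sample size, power and endpoints are unaffected. The change is worth making because it is a cheap safety gain. Confidence is moderate because the consent form and manuals could already contain the instruction.

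**What to change.** In section 5, Risks/Discomforts, keep the emergency steps first and unchanged. Extend the existing call sentence so that walkers also phone the research staff the same day after any of these:

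- exertional chest pain
- dyspnea that prevents talking
- dizziness that stops a session
- any emergency visit or admission

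Staff pass these reports to the study cardiologist, who decides whether exercise is held or adjusted. There is no automatic hold.

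Add one fixed adverse-event question to every existing call in both arms, so that adverse events are also asked about in the same way in each arm. If the consent form or manuals already carry the instruction, bring this paragraph into line with their wording.

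The cost is one extended sentence and one question on calls already planned, plus a few more reports and some cardiologist review time through week 58. With same-day reporting, awareness no longer depends on the call schedule, and the one-week limit can be met in every phase.

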#### 6. Participant Selection

Eligibility criteria: Inclusion criteria include: (a) men and women aged 50 to 89 who are diagnosed with HIV/AIDS and willing to participate; (b) Native English speaking; (c) live independently and within a 30-45 mile radius of Atlanta; (d) not involved in any structured exercise program or exercising 3 or more times per week for a minimum of 30 minutes; (e) not involved in any weight loss program (f) not hospitalized within the last 60-days; (g) clinically stable and on ART 6 months before enrollment; (h) if on statins medication they are stable for 3 months; (i) score 3 or less on the verbal memory subtest of the MoCA; or (j) < 0.5 SD below mean on the Oral Trail Making Test B; (k) able to provide informed consent and pass a consent post-test. Exclusion: (a) non sedentary (defined as engaging in > 30 minutes of moderately strenuous exercise 3 times or more a week); (b) medical or physical condition that would preclude participation in the exercise component of the study (e.g., severe arthritis or mobility problems, lower extremity amputations, joint replacement(s), balance disorders, dizziness, DOE with moderate exertion, difficulty walking one block, recent falls, obvious injury to lower extremity, uncontrolled hypertension or diabetes, renal failure, blindness, or a history of angina with activity); (c) ischemic changes or inappropriate BP changes on BL exercise (modified Balke or Bruce) treadmill test; (d) on oral corticosteroids (nasal, optical and inhaler corticosteroids allowed without restriction), experiencing acute inflammation at time of baseline or follow-up testing (this will result in rescheduling of testing if no other exclusion criteria apply after 2 weeks); (e) presence of current opportunistic infection; (f) any terminal illness; (g) regular use of anti-inflammatory medications such as non-steroidal anti-inflammatory agents excluding low dose aspirin; (h) on anti-psychotics; (i) on tricyclic antidepressants; (j) on anti-depressants equal to the equivalent of more than 1 mg of Clonazepam; (k) on Lithium; (l) women who are pregnant; (m) severe learning disabilities, intellectual disabilities, schizophrenia, bipolar, psychotic disorders to minimize confounding effects on neurocognitive data; (n) confounding neuro-medical conditions (e.g., active CNS opportunistic infections, seizure disorders, head injury with loss of consciousness greater than 30 minutes, intracranial neoplasms, stroke with neurological or neuropsychiatric sequelae, and non-HIV-associated dementias); (o) due to the high prevalence of Substance Use, Major Depressive and Generalized Anxiety Disorders in HIV disease individuals with histories of these three conditions will not be excluded; however, we will exclude individuals who meet criteria for any Substance Use Disorder or Major Depression within 6 months of evaluation (see Screening Interview below); (p) creatinine > 2.5 within the past 6 months; (q) PHQ-2 score > 4; (r) completed 8 years or less of school (s) failed to pass post-consent test after three attempts; (t) two or more positive drug screen tests (also PI discretion); (u) alcohol breathalyzer test result > 0.03; (v) PI discretion to withdraw research participants if the participant fails to maintain minimum research requirements. PI discretion for any inclusion or exclusion criteria listed above. Participants will be also recruited to ensure comparability across groups on demographic characteristics known to influence neuropsychological performance, including age, education, sex, ethnicity, and estimated premorbid Verbal IQ (using the American National Adult Reading Test-AMNART). The sample inclusion/ exclusion criteria were selected to eliminate conditions that would confound the dependent variables or interfere with participation in the interventions.

**Recruitment and enrollment** will occur through posted flyers in the recruiting clinics, through physician and nurse referral at the collaborating outpatient clinics. To facilitate referrals, study purpose and procedures will be discussed at clinical meetings, clinical and grand rounds, posted on research web sites, and during individual conferences with HIV providers at each of the enrolling sites by the investigative team. We will also arrange for regular recruitment events at the local recruitment clinics to distribute flyers and information about the study. There are also numerous support groups provided by the recruiting facilities and with permission we will distribute flyers and information about the study at those sessions. These strategies have been successful in our former and current studies. Potential participants may also be identified clinics and their medical records reviewed and contacted via research study recruitment letter.

The initial recruitment letter has an alphanumeric code which is a unique, randomly generated identifier that will be attached to a recruitment letter sent to each participant in the study. The identifier is structured (M-AA-##-AA) with the first letter indicating the recruitment site. The participants who receive a recruitment letter will be informed about the research study as well as given instructions to go online to a designated secure Version 02.15.2018 Page **16** of **30** 

website to accept or decline entrance into the study. Those that reply will be asked to enter their unique code ID#, DOB, and current phone number and select yes to be contacted or no to be removed from contact list. Of the participants that reply with interest in inclusion, within 3 business days research staff will contact them via the phone number given. Those that do not respond at all will receive a call within 1-2 weeks from a member of the research staff to verify interest. This information is stored on a secured server at the Emory School of Nursing, and any information obtained will only be used for the strict purpose of the approved study design. The subsequent recruitment letter will not contain the unique alphanumeric code, however the letter will still contain information about the study and staff contact information. Similar to before, those that do not respond will receive a call within 1-2 weeks from a member of the research staff to clinic patients will also be accompanied by a letter from the clinic staff declaring the collaboration between the clinic and the research team elevating any apprehension to legitimacy of the research and patient confidentiality.

In addition, [name] is PI of an ongoing study of adults living with HIV/AIDS called Project READ. READ includes patients from the same clinics proposed for recruitment/enrollment for this study – FiT BRAiN. As part of the informed consent process of project READ, participants can indicate if they are willing to be contacted for their interest in future studies led by the PI. For those persons who have indicated "yes" to this question and who are 50 years old or older, we will telephone them (based on their last known phone number) to inform them about the study and gauge their interest. If interested, the same screening procedures will take place.

Screening and Enrollment: The Project Coordinator or Recruiter will communicate biweekly with the clinic staff to remind them to refer potential HIV patients to be seen in the enrolling sites. Those interested and referred will be **Pre-Screened** either by phone or in person. Part of the pre-screen will provide verbal informed consent and then complete a Pre-Screening Interview. To rule out severe cognitive impairment or possible dementia that may interfere with study participation, the Montreal Cognitive Assessment (MoCA) memory subtest will be given. Those who score  $\leq 3$  on the MoCA will be eligible. In addition, the Oral Trail Making Test B will also be given. Those with < 0.5 SD will be eligible. Finally participants will asked "Have you been diagnosed with Major Depressive Disorder, Substance Use Disorder, or Anxiety Disorder in the past 6 months?" to rule out Substance Dependence and Major Depression in the previous 6 months. Those meeting the criteria for eligibility will be enrolled to the full study and scheduled for baseline

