# 4. Objectives

Our home-based aerobic exercise intervention, the '*Let's Move Program*' has been tested and is effective for lowering CVD risk in previous trials of older caregivers and adults with advanced CVD. The proposed efficacy trial, Fit BRAiN will recruit 200 PLWH and randomize them (2:1) to either the *Let's Move intervention* (n=132) or an attention control condition, *Let's Flex* (n=68), and follow them for an additional 3 assessments/time points (at 13-15 weeks post baseline, 28-30 weeks post baseline and again at 56-58 weeks post baseline). Participants will be  $\geq$  50 years of age, sedentary, demonstrate objectively measured CI, and stable on antiretroviral medications for at least 6 months. Motivational Interviewing (MI) will be used to promote exercise self-efficacy and optimize adherence to the intervention and flexibility and stretching to the attention control arm. The following are our aims:

AIM 1: To test, in a RCT, the efficacy of the *Let's Move Program* to improve cognitive functioning in this sample.

H0 1: Participants in the *Let's Move* intervention will have significantly higher scores than participants in the Let's Flex attention control group on measures of executive skill, episodic memory, and information processing speed at 3 assessments/time points (averaging a total of 56-58 weeks) post-baseline.

**AIM 2:** To test, in a RCT, the impact of the *Let's Move Program* on inflammatory markers, endothelial vascular function, and neuronal growth factor (BDNF) in this sample.

H0 2: Participants in the *Let's Move* intervention will demonstrate improved *inflammatory markers, neuronal growth factor, oxidative stress, thrombotic tendency, and endothelial vascular function* compared to the Let's Flex attention control group at 3 assessments/time points (averaging a total of 56-58 weeks) post-baseline.

**Secondary Aim:** To explore the potential mediation effects of inflammatory biomarkers, endothelial vascular function, and neuronal growth factor on the relationship between the *Let's Move Program* and the cognitive skills measured in Aim 1.

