# 5. Study Design and Methods

All procedures performed in this study are for research purposes only.

**FiT BRAIN Study Design**. We propose a 4-year, two-arm 2:1 RCT design to test the longitudinal effects of the Lets Move Program compared to an attention control group, the Lets Flex Program. We will accrue 160 participants, allowing for **20% attrition** over the course of the study, resulting in a final sample of **128 to be** 

randomized to one of the following 2 groups: Lets Flex (n=107) and Lets Move (n=53). Outcomes of interest include markers of CVD risk and cognitive functioning. Measures will be taken at Baseline, T1 (13-15 weeks post-baseline), T2 (28-30 weeks post-baseline), and T3 (56-58 weeks post-baseline). The ultimate goal of this study is lifestyle modification rather than a one-time intervention. The intervention is thus approached using behavioral change activation and maintenance strategies (e.g., motivational methods, long-term monitoring, and booster sessions).

Phase 1: Pre-enrollment preparation (0 - 9 months): Prior to initiating data collection, all recruitment, intervention materials, forms, and procedures will be refined and protocol manuals established. The recruitment and intervention materials will be reviewed by the Community Advisory Board (CAB) at the Ponce Infectious Diseases clinic for relevance, readability, cultural appropriateness, accuracy, and acceptability. Investigators will periodically retrain and assess adherence to intervention protocols by randomly selecting sessions to attend or phone calls to record and evaluate according to protocol quality indicators.

**Phase 2 (9-48 months) Implementation of the RCT.** We will conduct a 2 arm (Let's Move treatment condition vs. Let's Flex attention control condition) RCT among **160** sedentary OPLWH ages 40 and over who are stable on antiretroviral medications for at least 6 months and have cognitive impairment (see inclusion criteria below). Variables of interest will be measured at baseline, T1 (13-15 weeks post-baseline), T2 (28-30 weeks post-baseline), and T3 (56-58 weeks post-baseline).

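### The Oral Trail Making B entry cut-off is stated in two inconsistent ways, and a near-average score can satisfy it, so it does not secure the cognitively impaired sample the trial describes

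*Combined protocol and SAP*

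**What the plan says.** Sections 2 (Abstract) and 4 (Objectives) describe participants who "demonstrate objectively measured CI". Section 5 (Study Design and Methods, Phase 2) says they "have cognitive impairment (see inclusion criteria below"), so the eligibility criteria are the working definition of impairment.

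Section 6 (Participant Selection) gives that definition twice:

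- **Eligibility list, items (i) and (j).** The first route in is "score 3 or less on the verbal memory subtest of the MoCA; or (j"). The alternative, item (j), is "< 0.5 SD below mean on the Oral Trail Making Test B".
- **Screening and Enrollment.** The MoCA memory subtest is given, with low scores eligible. Then: "In addition, the Oral Trail Making Test B will also be given". The cut-off is "Those with < 0.5 SD will be eligible".

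The screening text gives the purpose of the MoCA subtest as "To rule out severe cognitive impairment or possible dementia that may interfere with study participation". Neither place names a normative source for Oral Trail Making B or says whether a high score is good or bad. People who pass pre-screening go straight to enrolment and a baseline appointment.

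**The concern.** This threshold helps decide whom the trial's conclusion applies to. Item (j) can be taken as a cap on the shortfall (less than half an SD below the mean) or as a score under the point half an SD below the mean. On this test, those two rules select opposite people. The screening text drops the reference to the mean altogether, and its literal meaning takes in everyone up to half an SD above average.

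The stated purpose of the MoCA subtest does not settle the direction. It speaks of excluding severe impairment, yet low scorers are the ones made eligible. If the wording is applied literally, the trial can enrol people with no demonstrated deficit and describe them as impaired.

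**Working it through.** The plan gives no figure for the share of people this criterion admits, so there is nothing to reproduce. The check sets out each reading and its size.

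**Input from the documents.** The cut-off of 0.5 SD, in the two wordings of section 6.

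**Assumptions (not in the documents).** The score is a normative z-score, normally distributed, with higher scores better. Φ is the standard normal distribution function: Φ(0.5) = 0.691, Φ(-0.5) = 0.309.

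**Unimpaired reference population (mean 0, SD 1).**

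| Reading | Source | Formula | Share admitted |
|---|---|---|---|
| z > -0.5 | item (j), as a cap on the shortfall | 1 - Φ(-0.5) | 69.1% |
| -0.5 < z < 0 | item (j), narrow: below the mean, by less than 0.5 SD | Φ(0) - Φ(-0.5) = 0.500 - 0.309 | 19.1% |
| z < +0.5 | screening text, literal | Φ(0.5) | 69.1% |
| \|z\| < 0.5 | screening text, as distance from the mean | Φ(0.5) - Φ(-0.5) | 38.3% |
| z ≤ -0.5 | item (j), probable intent | Φ(-0.5) | 30.9% |

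Every reading except the last admits near-average scores. Three of them (z > -0.5, -0.5 < z < 0 and |z| < 0.5) also exclude, on this test, everyone more than 0.5 SD below the mean.

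**Group with an assumed true mean of -1 SD.**

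- z > -0.5: 1 - Φ(-0.5 + 1) = 1 - Φ(0.5) = 30.9%.
- z ≤ -0.5: Φ(0.5) = 69.1%.

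The two readings of item (j) are complements, so the proportions reverse.

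**Effect of the and/or rule.** Let p be the share passing the MoCA criterion, which the documents do not give, and q the share passing Oral Trail Making B. Treat the tests as independent, use the unimpaired-population q, and let p run from 20% to 60%.

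- Either test, 1 - (1 - p)(1 - q): 75.3% to 87.7% admitted with q = 69.1%; 44.7% to 72.3% with q = 30.9%.
- Both tests, pq: 13.8% to 41.5% with q = 69.1%; 6.2% to 18.5% with q = 30.9%.

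**Is there a later check?** None is described.

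- The Table 4 battery is an outcome measure. It is given at the second baseline visit (section 5, Study Assessments), and randomisation comes before that visit (section 5, Randomization procedures).
- HAND diagnosis appears only as a possible covariate in the Aim 1 model (section 7).
- Section 6 leaves every criterion open to investigator discretion without a rule.

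**The case against.** The strongest reply is that the intent is clear. Item (j) parses naturally as a score under the point 0.5 SD below the mean. That matches item (i), where low scores qualify, and the repeated statement that participants are impaired. This stands as far as it goes: item (j) is ambiguous, and a reader who infers that it admits unimpaired people under any reading goes further than the text allows. It does not rescue the screening text, which omits the mean and the sign.

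The sentence "In addition, the Oral Trail Making Test B will also be given" may simply describe giving a second test, with each test carrying its own eligibility statement. That is compatible with the either-test rule, so a contradiction on and/or is not established. The screening text just does not repeat the rule.

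The 69% is for an unimpaired reference population. Section 3 puts HAND at 40-50% of people with HIV across ages and nearly twice as common in older people as in younger, so the people screened will probably score lower. That is why the -1 SD case is shown.

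Three stronger inferences are tempting and are not supported:

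- **A stated loss of power.** This needs the share of unimpaired people enrolled and the effect of exercise in them. The documents give neither, and section 3 cites cognitive gains from fitness training that are not confined to impaired people.
- **An efficacy question that cannot be answered.** Randomisation keeps the comparison fair under any reading, and the planned HAND covariate suggests that the sample's impairment could be described.
- **Different rules at the three clinics.** Section 5 calls them recruitment sites, and section 6 has them refer patients to the project's own coordinator or recruiter. Nothing says that the clinics score the test.

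**Conclusion.** The point holds as a defect in the entry threshold. The two statements of the Oral Trail Making B cut-off are inconsistent. The screening text, read literally, admits average performers, and item (j) allows opposite selections. Because either test suffices and nothing later confirms impairment, a near-average score on this test alone can qualify a person, contrary to the stated population.

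In an unimpaired reference population, z > -0.5 or z < +0.5 admits 69%, against 31% for z ≤ -0.5. At an assumed true mean of -1 SD, z > -0.5 admits 31% and z ≤ -0.5 admits 69%. These percentages rest on normality and on a higher-is-better z-score; the ambiguity of direction does not. Staff may already be applying the probable intent, but the documents do not show it.

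**What to change.** Put one signed criterion in both the eligibility list and the screening text, consistent with the stated aim of impairment and keeping the sponsor's own 0.5 SD; for example, at least 0.5 SD worse than the normative mean. Name the normative source and the direction of scoring. State in both places, in the same words, whether either test suffices or both are required. If screening has started, check the completed forms to see which rule was applied and report the result.

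The cost is a wording amendment, a review of screening forms and possibly a smaller eligible pool. The corrected cut-off still admits about 31% of an unimpaired reference population on this test, so it reduces the problem without removing it.
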